5.3.2. Prednisolone

Commercially available prednisolone 10 mg tablets will be provided by Gilead Sciences. Subjects will take 40 mg prednisolone (4 x 10 mg) orally with water, once a day, with or without meals. The study drug should be swallowed whole and taken at approximately the same time each day. A dose will be considered missed if the subject cannot take the dose within 8 hours of their regular dosing time. The timing of prednisolone dosing should remain unchanged in subjects on dialysis. If a subject misses a dose, the subject should take their next dose at the regular dosing time. Prednisolone administration will not exceed 28 days from Baseline/Day 1 (a tapering course of prednisolone after the 28-day treatment period will not be allowed).

5.4. **Prior and Concomitant Medications**

In vitro data suggests that GS-4997 has the potential to inhibit P-glycoprotein (P-gp). GS-4997 has the potential to increase the exposure of sensitive P-gp substrates (eg, aliskiren, dabigatran etexilate, digoxin, fexofenadine, ranolazine). In a drug-drug interaction study of GS-4997 co-administered with digoxin (0.5 mg), exposure of digoxin (AUC) was increased by less than 30%. GS-4997 may increase the exposure of other P-gp substrates; however, the clinical relevance of such interactions has not been determined. Co-administration of P-gp substrates with study drug is allowed, with specific guidance provided for the following:

- Digoxin: Follow digoxin level at baseline and at the Week 1 visit with digoxin level checks during the study period per investigator discretion (as frequently as needed).
- Dabigatran etexilate: Consult Medical Monitor
- Ranolazine: Monitor for side effects
- Aliskiren: Use with caution, dose may need to be reduced

All concomitant medication will be recorded in the source documents. This includes concomitant medications taken within 30 days prior to Screening and any taken during the study to the end of

the follow-up period. Enteral and parenteral nutritional products administered during the study will be recorded on eCRFs.

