7.5. Toxicity Management

Treatment-emergent toxicities will be noted by the Investigator and brought to the attention of the Medical Monitor. Whether or not considered treatment-related, all subjects experiencing AEs must be monitored periodically until symptoms subside, any abnormal laboratory values have resolved or returned to baseline levels or they are considered irreversible, or until there is a satisfactory explanation for the changes observed.

Administration of all study drugs may be discontinued due to a clinical or laboratory adverse event. Subjects are allowed to take one study drug and not the other.

Prednisolone may be dose-reduced or interrupted at the discretion of the investigator (e.g. due to new-onset, severe sepsis or diabetes mellitus that cannot adequately be controlled). Prednisolone should be discontinued in subjects with a Lille Score ≥ 0.56 at Day 7 (null responders); these subjects may continue GS-4997/placebo treatment. Except in Lille Score null responders, restarting prednisolone may be considered if the reason for interruption has resolved or become adequately controlled in the opinion of the investigator within 7 days of prednisolone interruption. Any decision to restart prednisolone must be reviewed with the Medical Monitor.

There is no option for GS-4997/placebo dose reduction, but GS-4997/placebo may be interrupted due to drug-related toxicity (see below). If GS-4997/placebo is interrupted, it may be restarted on

a case by case basis if the reason for interruption has resolved or become adequately controlled in the opinion of the investigator within 7 days of GS-4997/placebo interruption. Any decision to discontinue or restart GS-4997/placebo must be reviewed with the Medical Monitor.

Subjects who meet any of the following criteria must stop GS-4997/placebo

- Laboratory Criteria (based on central laboratory data):
 - Total bilirubin > 3x Baseline/Day 1 or nadir (confirmed by immediate repeat testing)
 - ALT and/or AST > 5x Baseline/Day 1 (confirmed by immediate repeat testing), unless the elevation is thought by the Principal Investigator to be secondary to an etiology other than GS-4997-related, drug-induced liver injury (e.g. infection).

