# 4.2.2. Adherence to Study Drug

The level of protocol defined adherence to each of the 2 study drugs will be determined by the total amount of study drug administered relative to the total amount of study drug expected to be administered based on what is specified in the protocol.

The level of adherence will be expressed as a percentage using the following formula:

On-Treatment Adherence (%) = 
$$\left(\frac{\text{Total Amount of Study Drug Administered}}{\text{Study Drug Expected to be Administered on Treatment}}\right) \times 100$$

Total amount of study drug administered will be the total number of pills dispensed minus the total number of pills returned. If a bottle (selonsertib/placebo) or carton (prednisolone) of study drug is not returned, the subject will be assumed to have not taken the pills.

Subjects are expected to take 28 tablets containing SEL (18 mg)/PLA and 112 tablets containing 10 mg of PRED; unless the subject is prematurely terminated from study drug due to death, lack of efficacy (meeting Lille score criteria [ie,  $\geq 0.56$  at Week 1 for prednisolone; or > 0.85 at Weeks 1, 2, 3, or 4 for both study drugs]), or does not have biopsy-proven severe AH on biopsy (ie, variable SDRGREAS\_STD equal to 'PW', 'PV', 'LE, or 'DT' on the study drug completion eCRF for an individual study drug and subject). Subjects who were transplanted while on study drug (eg, Subject ID PPD should also only have adherence calculated to their last dose date of study drug. Note that no subjects in the study had positive results for HBsAg, HCV RNA or HIV-1/HIV-2 per central laboratory assessment which was also a criteria for calculating adherence to last dose date. Subjects who do not complete individual study drug completion form, will have adherence for that study drug calculated to last dose date of individual study drug.

In addition, subjects meeting individual SEL/PLA subject stopping criteria for the study (eg, Grade 3 or higher treatment-emergent AE that is considered to be related to study drug and results in premature discontinuation of SEL/PLA, confirmed ALT or AST > 5 x baseline, confirmed total bilirubin > 3 x baseline or nadir, or ALT or AST > 500 U/L) who prematurely discontinued SEL/PLA will have adherence for SEL/PLA calculated to their last dose date of SEL/PLA (ie, Subject ID PPD for confirmed ALT > 5 x baseline).

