## 4.3. Protocol Deviations

Subjects who did not meet the eligibility criteria for study entry, but were randomized into the study will be summarized regardless of whether they were exempted by the sponsor or not. The summary will present the number and percentage of subjects who did not meet at least 1 eligibility criterion and the number of subjects who did not meet specific criteria by treatment group based on the Safety Analysis Set. A by-subject listing will be provided for those subjects who did not meet at least 1 eligibility (inclusion or exclusion) criterion. The listing will present the eligibility criterion (or criteria if more than 1 deviation) that the subject did not meet.

Protocol deviations occurring after subjects entered the study are documented during routine monitoring. The number and percentage of subjects with important protocol deviations by deviation reason (eg, nonadherence to study drug, violation of select inclusion/exclusion criteria) will be summarized by treatment group for the Safety Analysis Set. A by-subject listing will be provided for those subjects with any protocol deviation.

The last chronologic screening laboratory result from Covance and the screening value from the local laboratory for AST (U/L), ALT (U/L), AST/ALT ratio, total bilirubin (mg/dL), serum creatinine (mg/dL), INR, prothrombin time (PT) in seconds, PT control (seconds), calculated MELD, calculated Maddrey DF, and serology testing (HbsAg, HCV Ab, HCV RNA, HIV-1/2 Ab) will be provided. Subject IDs PPD and PPD used central laboratory values to determine eligibility (under protocol Amendment 1) while all other subjects utilized local laboratory values. Subject ID PPD enrolled under Amendment 1 and was assessed for eligibility using local labs (protocol violation).

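### SAP 4.2.2 counts tablets withheld under the protocol's own interruption and dose-reduction provisions as non-adherence, and does not say clearly whether AE-driven prednisolone stops are excused

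*SAP*

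**What the plan says.** SAP 4.2.2 defines adherence as the amount administered divided by the amount expected under the protocol, times 100, and labels the formula on-treatment.

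- **Numerator:** "Total amount of study drug administered will be the total number of pills dispensed minus the total number of pills returned".
- **Denominator:** "Subjects are expected to take 28 tablets containing SEL (18 mg)/PLA and 112 tablets containing 10 mg of PRED".
- **Listed exceptions:** the full count applies "unless the subject is prematurely terminated from study drug due to death, lack of efficacy" by the Lille criteria, or absence of biopsy-proven AH. These are identified by four reason codes, of which PW and PV are not defined. Transplant while on drug also ends the count at the last dose. Positive serology would have done so too, but the SAP notes that none occurred.
- **Completion-form sentence:** it ends the count at the last dose for subjects who do not complete the individual study drug completion form. The wording is broken.
- **Stopping-criteria paragraph:** subjects meeting a SEL/PLA stopping criterion "who prematurely discontinued SEL/PLA will have adherence for SEL/PLA calculated to their last dose date of SEL/PLA". Prednisolone is not mentioned there.

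The SAP reports descriptive statistics and the ≥ 80% count for each drug (4.2.2), and the proportion at ≥ 80% for both drugs (4.2).

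On dosing, Protocol 5.3.2 says "Subjects will take 40 mg prednisolone (4 x 10 mg) orally with water, once a day" and "Prednisolone administration will not exceed 28 days from Baseline/Day 1". Protocol 7.5 adds: "Prednisolone may be dose-reduced or interrupted at the discretion of the investigator". It also allows any study drug to be stopped for an AE, and SEL/PLA to be interrupted (not reduced) for drug-related toxicity. For either drug, a restart may be considered if the cause resolves or is controlled within 7 days. Protocol 6.9.9 raises prednisolone interruption in documented infection.

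**The concern.** The label and the denominator do not match. Prednisolone cannot run past 28 days from Day 1, so tablets withheld during a permitted interruption cannot be made up. For that subject 112 is out of reach, however carefully the prescription is followed. The SAP already excuses several directed stops, so its evident principle is not to score directed withholding as missed tablets. It does not carry that principle through to reductions and interruptions.

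This matters because adherence is one of only two exposure measures in SAP 4.2. The other, duration in 4.2.1, ignores temporary interruptions by definition. The adherence percentage is therefore the exposure summary that registers them, and it mixes withheld tablets with tablets the subject failed to take. If one arm has more AE-driven changes, it will look less adherent for that reason. In a trial whose primary objective is safety, that could be misread as subject behaviour.

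**Working it through.** **Inputs.** Prednisolone 4 tablets a day for at most 28 days (Protocol 5.3.2). SEL/PLA 1 tablet a day for 28 days (Protocol synopsis). Expected counts of 112 and 28, and the 80% line (SAP 4.2 and 4.2.2). Restart window of 7 days (Protocol 7.5). Assumptions: every prescribed tablet is taken, all containers are returned, and withheld days are not made up.

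**1. Reproduce the SAP's counts.** 4 × 28 = 112 and 1 × 28 = 28. Both agree.

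**2. Locate the 80% line.** 0.80 × 112 = 89.6, so at least 90 prednisolone tablets are needed. A subject falls below once 112 − 89 = 23 or more are withheld (89/112 = 79.5%).

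**3. Full interruption of d days, then restart.** Adherence = (112 − 4d)/112.

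| Days interrupted | Tablets taken | SAP adherence | Against tablets prescribed |
|---|---|---|---|
| 5 | 92 | 82.1% | 100% |
| 6 | 88 | 78.6% | 100% |
| 7 | 84 | 75.0% | 100% |

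For SEL/PLA the formula is (28 − d)/28, which gives the same percentages: 23/28 = 82.1%, 22/28 = 78.6%, 21/28 = 75.0%. A 7-day interruption, the limit for considering restart, is enough on its own to cross the line.

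**4. Reduction.** The protocol states no reduced dose, so this is arithmetic only. The line is crossed after 23 days with one tablet a day withheld (89/112 = 79.5%), 12 days with two (88/112 = 78.6%), or 8 days with three (88/112 = 78.6%).

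**5. AE-driven prednisolone stop, if not excused.** Adherence = 4 × (last dose day)/112.

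| Last dose day | Tablets taken | SAP adherence |
|---|---|---|
| 7 | 28 | 25.0% |
| 10 | 40 | 35.7% |
| 14 | 56 | 50.0% |
| 22 | 88 | 78.6% |
| 23 | 92 | 82.1% |

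**6. Is it excused?** Read literally, the completion-form sentence covers only subjects with no completed form, so an AE stop keeps 112. Read as covering anyone who did not complete that drug, it excuses AE stops, but the listed exceptions and the SEL/PLA paragraph would then be redundant. The undefined codes do not settle it. Neither reading reaches reductions or interruptions followed by a restart, so steps 3 and 4 stand either way.

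**The case against.** The strongest reply is that this is an openly defined planned-course denominator in a descriptive table. Adherence defines no analysis set and enters no test. The causes are visible elsewhere by arm: reasons for stopping each drug (SAP 4.1), and TEAEs leading to prednisolone discontinuation, interruption or modification (SAP 7.1.6; Tables 15.11.5.2, 15.11.5.5 and 15.11.5.6). That limits the harm, and it stands. It does not rescue the number. The SAP does not label it as a share of the planned course, and those AE tables cannot be netted out of the ≥ 80% counts.

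Some stronger readings are tempting but not supported:

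- **That the two drugs are scored on different principles.** Only SEL/PLA is named in the stopping-criteria paragraph. However, prednisolone's own individual stopping criterion, Week 1 Lille ≥ 0.56, also shortens its denominator. The text fits a split between mandated and discretionary stops as well as it fits a split between drugs.
- **That permitted changes become protocol deviations.** SAP 4.3 summarises deviations by "deviation reason (eg, nonadherence to study drug, violation of select inclusion/exclusion criteria". It says they are documented during routine monitoring, and nothing ties them to this percentage or the 80% line.
- **That the problem will be common.** Protocol 1.1 cites infections in 52% of corticosteroid-treated patients in one cohort. That is not a rate of prednisolone changes, and interruption for infection is discretionary. The documents give no rate of changes and no difference between arms.
- **That every directed change produces a sub-80% subject.** Interruptions of up to 5 days, AE stops with a last dose on Day 23 or later, and short reductions stay at or above 80%, although they still lower the mean.

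**Conclusion.** The point holds for protocol-permitted prednisolone reductions and interruptions, and for permitted SEL/PLA interruptions. A subject who takes every prescribed tablet is counted below 80% after 6 or more full days of interruption (78.6% at 6 days, 75.0% at 7). For AE-driven prednisolone stops the SAP is unclear. If they are not excused, a last dose on or before Day 22 has the same result.

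The affected outputs are the adherence means and the ≥ 80% counts for each drug and for both. How many subjects are affected, and whether the arms differ, cannot be derived from the documents. As an upper bound, an excess of x percentage points in one arm of subjects losing 23 or more directed tablets lowers that arm's ≥ 80% prednisolone figure by at most x points. The results assume complete tablet counts and no making up of withheld days. No inference in the trial rests on these figures, but the rule returns a wrong value for the quantity it names and should be corrected.

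**What to change.** In SAP 4.2.2:

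1. Compute on-treatment adherence for each drug against tablets prescribed. Count up to that drug's last dose date for AE-driven and other investigator-directed stops, net of investigator-directed interruptions and reductions. Identify these from the study drug administration and AE action-taken records.
2. Do not shorten the denominator for stops due to subject noncompliance or subject request (both listed in Protocol 6.8). Excusing those would remove the non-adherence the measure is meant to show.
3. Rewrite the completion-form sentence to say which stops it covers, and define PW and PV.
4. Report the percentage of the full planned 28 and 112 tablets as a separate row, labelled as such.

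The cost is one small derivation and a table row. The documents do not show that the eCRF records the prescribed daily dose. If it does not, reductions must be identified from AE action-taken data or footnoted. Dosing gaps with no matching AE action cannot be told apart from missed doses and need the same footnote. The trial was already unblinded for the primary analysis (SAP 2.3), so showing both rows also avoids any appearance of choosing between them. If the SAP is already final, SAP section 1 provides for recording the change in the CSR. No dosing or stopping rule changes.

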## 4.3. Protocol Deviations

Subjects who did not meet the eligibility criteria for study entry, but were randomized into the study will be summarized regardless of whether they were exempted by the sponsor or not. The summary will present the number and percentage of subjects who did not meet at least 1 eligibility criterion and the number of subjects who did not meet specific criteria by treatment group based on the Safety Analysis Set. A by-subject listing will be provided for those subjects who did not meet at least 1 eligibility (inclusion or exclusion) criterion. The listing will present the eligibility criterion (or criteria if more than 1 deviation) that the subject did not meet.

Protocol deviations occurring after subjects entered the study are documented during routine monitoring. The number and percentage of subjects with important protocol deviations by deviation reason (eg, nonadherence to study drug, violation of select inclusion/exclusion criteria) will be summarized by treatment group for the Safety Analysis Set. A by-subject listing will be provided for those subjects with any protocol deviation.

The last chronologic screening laboratory result from Covance and the screening value from the local laboratory for AST (U/L), ALT (U/L), AST/ALT ratio, total bilirubin (mg/dL), serum creatinine (mg/dL), INR, prothrombin time (PT) in seconds, PT control (seconds), calculated MELD, calculated Maddrey DF, and serology testing (HbsAg, HCV Ab, HCV RNA, HIV-1/2 Ab) will be provided. Subject IDs PPD and PPD used central laboratory values to determine eligibility (under protocol Amendment 1) while all other subjects utilized local laboratory values. Subject ID PPD enrolled under Amendment 1 and was assessed for eligibility using local labs (protocol violation).

# 5. **BASELINE CHARACTERISTICS**

# 5.1. Demographics

Subject demographic variables (ie, age, sex, race, and ethnicity) will be summarized by treatment group and overall using descriptive statistics for age, and using number and percentage of subjects for age ( $< 50, \ge 50$  years), sex, race, and ethnicity. Age at baseline is calculated in years at the first dosing date of study drug. If a subject did not receive study drug after randomization, the subject's age will be calculated from the baseline assessment date. For screen failures, age will be calculated from the date of informed consent. The summary of demographic data will be provided for the Safety Analysis Set and for the Full Analysis Set.

A by-subject demographic listing, including the date of informed consent, will be provided by subject ID number in ascending order.

## 5.2. Other Baseline Characteristics

Prior alcohol consumption (g/day) before acute AH event, weight (kg), height (cm), and BMI (kg/m^2) as a continuous and categorical (< 25, 25 to < 30 and  $\ge 30$  kg/m^2) variable will be summarized separately by treatment group and sex and sex overall.

**Baseline characteristics** for the study will include the following:

- Baseline height (cm)
- Baseline weight (kg)
- Baseline BMI  $(kg/m^2)$
- Baseline BMI (< 25, 25 to < 30 and  $\geq$  30 kg/m^2)
- Prior alcohol consumption (g/day) before the acute AH event
- Alcohol Use Disorders Identification Test (AUDIT) as a continuous variable
- AUDIT as a categorical variable (< 8 [does not meet criteria]; ≥ 8 and <13 for women or

   <15 for men [harmful or hazardous drinking]; ≥ 13 for women, ≥ 15 for men [alcohol dependence])

- Severity of Alcohol Dependence Questionnaire (SADQ) as a continuous variable
- SADQ as a categorical variable (<16 [mild physical dependency]; 16-30 [moderate dependence];  $\geq$  31 [severe alcohol dependence])
- Method of liver biopsy (percutaneous, transjugular, missing)

- Biopsy consistent with AH diagnosis (yes, no)
- Fibrosis assessment method (Metavir-equivalent, Ishak, Not Available)
- Fibrosis score as a subcategory to the fibrosis method (ie, Metavir-equivalent [F0, F1-F2, F3, F4] or Ishak [F0, F1-F2, F3-F4, and F5-F6])
- Baseline ascites (none, mild/moderate [or diuretic responsive], severe [or diuretic refractory])
- Baseline hepatic encephalopathy (none, grade 1-2 [medication controlled], grade 3-4 [medication refractory])
- Hospitalized at screening (yes, no)
- Days hospitalized prior to first dose date. Calculated as: (minimum of [date of first dose of study drug, date of release] hospital admission date) +1 for subjects hospitalized at screening
- Baseline pyrexia (baseline temperature ≥ 38° C, ≥ 100.4° F [yes] or < 38° C, < 100.4 ° F [no])

- Baseline infection (yes, no) as recorded on the medical history eCRF.
- Treatment for baseline infection (yes, no) as recorded on the medical history eCRF
- Evidence of baseline infection on chest X-ray (yes, no)
- Baseline MELD score (as a continuous variable)
- Baseline CPT score (as a continuous variable)
- Baseline CPT class (A [scores of 5-6], B [scores of 7-9], C [scores of 10-15])
- Baseline Maddrey DF score (as a continuous variable)
- Baseline AST (U/L)
- Baseline ALT (U/L)
- Baseline AST/ALT Ratio
- Baseline total bilirubin (mg/dL)
- Baseline direct bilirubin (mg/dL)
- Baseline GGT (U/L)

- Baseline albumin (g/dL)
- Baseline alkaline phosphatase (U/L)
- Baseline INR
- Baseline serum creatinine (mg/dL)

